Many methods have been proposed to avoid coughing during extubation with variable success rates. The most promising method involves using remifentanil, an ultra-short acting opioid, with an advanced medication-delivery system that is not available in the U.S. We have recently demonstrated how to replicate the performance of this system using a standard medication pump and an algorithm that can be run on a spreadsheet or mobile app.

(2) The purpose of this study is to determine whether using remifentanil with our algorithm can in fact decrease or prevent coughing around the time of extubation. For eligible patients we will randomly administer remifentanil or a placebo in their intravenous line at the time that surgery is concluding. An independent observer will then determine whether or not the patient coughed at the end of surgery and qualify the intensity of the cough.

PURPOSE AND OBJECTIVES

Purpose: The importance of the research and the potential knowledge to be gained should be explained in detail. Give background information.

At the end of surgical procedures, for patients who have had general anesthesia, an endotracheal tube (ETT) is removed ("extubation") from a patient's trachea during emergence from general anesthesia. Extubation can be performed either while the patient remains deeply anesthetized or, more commonly, when the patient has a return of protective airway reflexes. These reflexes include coughing as a result of the stimulation from the ETT on the glottis and the trachea. While it is common for coughing to occur, it is usually not dangerous and has minimal effect on surgical outcomes. However, there are certain surgical procedures where coughing can have a detrimental effect. Examples that have been reported included bleeding into the neck

following ear, nose, and throat surgery, which can cause compression of the trachea; and bleeding into the retina following ophthalmological procedures.

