Of all the different methods described in the literature, only the administration of remifentanyl, an ultra-short-acting opioid, showed any promise at decreasing the occurrence of coughing on emergence. All the published studies described using remifentanyl with a target-controlled-infusion (TCI) pump in order to achieve a specific concentration of the medication at its site of action ("effect site concentration"). In fact, most studies [1-6 and 8-9] recommend achieving a target effect site concentration from 1.5 to 2.5 ng/mL with varying levels of success achieved. Lee [1] identified that an effect site concentration of 2.14 ng/mL would have a 95% success at preventing coughing. A single study [7] described giving a bolus of remifentanyl but was unsuccessful at decreasing the incidence and frequency of coughing. These studies are not able to be replicated in the United States as TCI pumps are not cleared for use by the FDA. No modern TCI pump manufacturer has filed or is likely to file an application with the FDA, and hence the pumps are not available for use in the U.S.

Remifentanyl is particularly useful medication for this application given its safety profile and duration of action. Per the drug label information as submitted to the FDA, spontaneous respiration occurs at blood concentrations of 4 to 5 ng/mL in the absence of other anesthetic agents [10]. (This is twice the dose that will be administered in this study, and while other opioids may be prescribed with the potential to cause respiratory depression, in this study extubation will only occur once sufficient ventilation is demonstrated by the patient. Should respiratory depression or emergence from anesthesia cause more than 15 minutes of delay from the end of the case, the remifentanyl infusion will be stopped). In addition, recovery from anesthesia was rapid, predictable, and independent of the duration of the infusion [10] with a rapid elimination rate: the context-sensitive half-times is approximately 3 to 6 minutes. In the manufacturer clinical submission, no case of remifentanyl-induced delayed respiratory depression occurring more than 30 minutes after discontinuation of remifentanyl was found[10]. Finally, the addition of supplemental opiates for post-operative pain control did not delay recovery of respiratory drive in patients undergoing major surgery with remifentanyl-propofol total IV anesthesia [10].

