The reason why using a TCI pump is necessary for this goal is due to the need for a precise therapeutic window for the opioid: insufficient dose will result in inadequate effect, and excess dose can lead to respiratory depression and prolonged emergence from anesthesia. While there is a certain amount of variability in the pharmacokinetics of drugs within a population, using a TCI pump will decrease the variability [11], therefore allowing for more accurate titration of the drug. This is one of the reasons why the studies that used TCI pumps [1-6] and [8-9] were successful at preventing coughing while the study that used bolus dosing alone [7] was not.

Understanding the pharmacokinetic properties of remifentanyl, we have created an algorithm that can be implemented on a spreadsheet and which can be programmed into a standard infusion pump in a manner that remains consistent with its direction for use. The algorithm calculates a remifentanyl bolus and infusion rate, based on the patient's characteristics (age, weight, height and sex), that can achieve a desired effect site concentration. While not being a TCI system proper, we have demonstrated through simulation that this algorithm can reasonably replicate the performance of a Target Controlled Infusion pump[12]. This would negate the need for specialized devices and allow U.S. anesthesiologists access to a technology the rest of the world has employed safely for two decades. This algorithm is available to use and download for free at the following website: <http://bit.ly/2lXH0m8>. The purpose of our study is to determine whether our algorithm can prevent coughing with emergence and replicate the results obtained previously with a TCI pump.

References. Include references to prior human or animal research and references that are relevant to the design and conduct of the study.

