Study coordinators will identify and consent the appropriate patient on the day of surgery. Patient who agree to participate in the study will be randomized to receiving either a placebo or remifentanyl in a syringe that will be blinded to the patient, the clinicians in the room as well as the study coordinator. Once the patient is in the OR, the setup which includes the syringe, the BBraun Perfusor Space syringe pump and extension tubing will be connected the IV tubing at the most proximal port to the patient. The study coordinators will then input the patient's characteristic into the spreadsheet containing the algorithm, set for a goal remifentanyl effect site concentration of 2.1 ng/mL, and program the syringe pump under the guidance and supervision of anesthesia provider in the room. The study pump will be maintained in a "standby" mode until activated as described below. During the induction and maintenance of anesthesia, the provider has full liberty to manage the anesthetic plan.

In approximately the last 5-30 minutes of surgery, as identified by the surgeon, the infusion pump will start infusing as was previously programmed. Patients whose surgery will end less than 5 minutes prior to the start of infusion, or, patients who will be extubated while deeply anesthetized will be excluded from the study and will not receive any of study drug or placebo. At the conclusion of the surgery, the anesthetic gases will be discontinued, any neuromuscular blocking agent reversed, and, when clinically indicated the patient will be extubated and monitored for adequate respiratory effort. The infusion will be terminated either when the patient is extubated, or at 15 minutes after the start of anesthetic washout. Anesthetic washout occurs at the end of surgery when the anesthetic gases are turned off and high flows of oxygen are administered to purge the residual anesthetic from the system and the patient. The anesthesia provider will ensure suitability for transfer to the post-anesthesia care unit at all times as per usual clinical practice. The study period will conclude once the patient is discharged from direct anesthesia care.

The study coordinators will be tasked with documenting:

- 1) The incidence of cough
- 2) If coughing present, the cough will be graded according to the following scoring guidelines:
 - a. 0=no cough
 - b. 1=slight cough, cough without obvious contraction of the abdomen

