 - c. 2=moderate cough, strong and sudden contraction of the abdomen lasting for less than 5 seconds

Research Protections Office, [name], [contact]

d. 3=severe cough, strong and sudden contraction of the abdomen sustained for more than 5 seconds.

The above scoring will be assessed at the following four stages of extubation:

- a. eyes opening on verbal commands
 - b. tracheal cuff deflation
 - c. tracheal extubation
 - d. 1 min after extubation.
- 3) Extubation time: time between the termination of the anesthetic and extubation
 - 4) Time to recovery: time between extubation and the ability to perform purposeful movement (e.g. squeeze hand, thumbs up. Anesthesia providers ask patients to perform a purposeful movement as part of routine care.)
 - 5) Adverse events including hypoxemia despite oxygen supplementation and other respiratory complications such as laryngospasm, upper airway obstruction requiring intervention: bag mask ventilation, oral or nasal airway insertion.

Also documented will be the duration of the infusion and quantity of drug administered.

For research involving survey, questionnaires, etc.: Describe the setting and the mode of administering the instrument and the provisions for maintaining privacy and confidentiality. Include the duration, intervals of administration, and overall length of participation. (describe and attach all instruments)

Not applicable

Statistical Considerations: Delineate the precise outcomes to be measured and analyzed. Describe how these results will be measured and statistically analyzed. Delineate methods used to estimate the required number of subjects. Describe power calculations if the study involves comparisons. Perform this analysis on each of the primary and secondary objectives, if possible.

As this a comparative study, the measure outcomes described above will compared as follows:

- 1) The incidence of cough will be analyzed with a Fisher Exact Test
- 2) The coughing grade will be analyzed with a Mann-Whitney U test
- 3) Extubation time and time to recovery will be analyzed with an unpaired t-test, if appropriate
- 4) Adverse events will be categorized and then analyzed with a Fisher Exact Test

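### Time to recovery is clocked from extubation, an event the study drug may itself shift, so on its own it can misstate a delay in responsiveness in either direction

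*Protocol*

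**What the plan says.** The Procedures section lists what the coordinators record. Item 3 is "Extubation time: time between the termination of the anesthetic and extubation". Item 4 is "Time to recovery: time between extubation and the ability to perform purposeful movement". Statistical Considerations assigns both to an unpaired t-test, if appropriate. They are the two timing outcomes that bear on secondary objective 3, time to emergence from anesthesia.

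Other statements bear on whether extubation is a neutral starting point:

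- The Purpose section warns that "excess dose can lead to respiratory depression and prolonged emergence from anesthesia". It also makes extubation conditional on adequate ventilation, and it provides for the case where respiratory depression or "emergence from anesthesia cause more than 15 minutes of delay from the end of the case".
- Procedures starts the infusion in roughly the last 5-30 minutes of surgery and leaves extubation to clinical indication. It then states: "The infusion will be terminated either when the patient is extubated, or at 15 minutes after the start of anesthetic washout".
- Procedures also states that "patients who will be extubated while deeply anesthetized will be excluded from the study". The Purpose section describes the usual alternative as extubation "more commonly, when the patient has a return of protective airway reflexes".

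**The concern.** A comparison of times between randomized arms is easiest to interpret when the clock starts at an event that treatment cannot move. Extubation is not such an event. It follows the start of the study drug and depends on ventilation and wakefulness, both of which an opioid may affect. If remifentanil makes extubation later, the item 4 clock starts later in that arm and the interval shortens, even when patients become responsive no sooner. There is also a possible push the other way: an infusion that runs until extubation begins to wear off just where the clock starts, which may lengthen the interval. The net direction cannot be told from the protocol.

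A second difficulty is that deep extubations are excluded. In a patient extubated awake, purposeful movement may come before the tube is out, and so before the clock starts. Eye opening to command is listed first among the four cough-scoring stages, ahead of cuff deflation and extubation. The protocol does not show how often this would happen.

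What is at stake is the reading of a secondary outcome on slower recovery, which is a natural trade-off of giving an opioid at emergence.

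**Working it through.** **Inputs.** The definitions of items 3 and 4 come from Procedures. The protocol gives no expected difference or standard deviation for either interval, so every minute value below is an assumption. There is no stated figure to reproduce.

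**Identity.** For each patient let

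- M = termination of the anesthetic to purposeful movement,
- E = termination of the anesthetic to extubation (item 3),
- R = extubation to purposeful movement (item 4).

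Then R = M - E. Writing d for remifentanil minus placebo, dR = dM - dE. Item 4 gives the true delay in movement only when dE = 0.

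**Numbers in (minutes).**

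| Assumed dM | Assumed dE (item 3 reads) | dR = dM - dE (item 4 reads) | Item 4 read alone |
|---|---|---|---|
| +3 | -1 | 3 - (-1) = +4 | exaggerated |
| +3 | 0 | 3 - 0 = +3 | correct |
| +3 | +1 | 3 - 1 = +2 | understated |
| +3 | +3 | 3 - 3 = 0 | cancelled |
| +3 | +5 | 3 - 5 = -2 | reversed |
| 0 | +3 | 0 - 3 = -3 | apparent gain |

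A comparison on M itself reads +3 in the first five rows and 0 in the last.

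**What a t-test would do.** This was simulated with 25 patients per arm (half of the 50 in the sample-size statement). Assumptions: E with control mean 10 and SD 3, R with control mean 3 and SD 2, E and R independent, dM = 3, 4,000 replicates, two-sided 5% level.

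| dE | Mean dR | t-test on R rejects | t-test on E + R rejects |
|---|---|---|---|
| 1.5 | 1.5 | 74% | 83% |
| 3 | 0.0 | 6% | 83% |
| 5 | -2.0 | 93%, with the mean difference in the wrong direction | 83% |

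The rates depend on the assumed SDs and on independence. The pattern follows from the identity.

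**Movement before extubation.** If M < E, then R = M - E is negative. If such a case is recorded as zero, or movement is looked for only after extubation, then E + R cannot fall below E. It therefore exceeds M, and the earlier response is lost.

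**The case against.** The strongest reply is that the two intervals sit side by side and join end to end, so nobody need read item 4 alone. In every row of the first table items 3 and 4 add up to dM, and in the cancelled and reversed rows item 3 shows +3 and +5, so a planned test would reveal the delay. On this view only a named sum is missing, and an analysis plan could supply it. That stands in part, and it is why the concern is limited to item 4 read by itself. It does not settle the matter. The sum recovers M only if movement follows extubation, or if an earlier movement is recorded at its own time. An analysis plan cannot restore a time that was never noted.

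A second reply is that extubation-to-movement is a coherent quantity in its own right: how long a patient is extubated but not yet responsive. That is true, and the interval is worth describing. As a between-arm measure of recovery, it still carries whatever the drug does to extubation.

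Third, termination of the anesthetic also falls after randomization and after the infusion starts. That is correct, but Procedures ties it to the conclusion of surgery, whereas extubation waits on the patient's ventilation and emergence. It is the sounder origin, though not a perfect one.

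Finally, the sizes are assumed. The warning about prolonged emergence concerns excess dose, the 15-minute provisions are contingencies rather than forecasts, and the protocol describes recovery from remifentanil as rapid. All of this stands, so neither the size nor the direction of any distortion can be claimed.

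**Conclusion.** The concern holds. As defined, the between-arm difference in time to recovery equals the drug's effect on time to movement minus its effect on time to extubation. Read by itself it can understate, cancel, reverse or exaggerate a delay in responsiveness, and it is right only if the drug leaves extubation time unchanged. With an assumed true delay of 3 minutes and assumed extubation shifts from -1 to +5 minutes, it ranges from +4 to -2.

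The identity is certain. The minute values are illustrations, and the frequency of movement before extubation is unknown. The reach is limited: the primary cough outcome is untouched, and secondary objective 3 is only partly affected because extubation time has a suitable origin. The change should be made, but the trial does not stand or fall on it.

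**What to change.** Redefine time to recovery as the interval from termination of the anesthetic to first purposeful movement on request, whether that comes before or after extubation, and compare the arms on that interval. Keep extubation time (item 3) as a separate outcome. The extubation-to-movement interval can still be derived and described.

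The cost is one line of the outcome definition. The anesthetic-off time is already needed for item 3, and the protocol notes that "Anesthesia providers ask patients to perform a purposeful movement as part of routine care". The coordinator must also note the time of the first response when it precedes extubation. That is a small extra observation while cough is being scored, and it depends on when the provider asks. The other downside is that extubation-to-movement is no longer the headline measure. Clinical care does not change. The definition should be settled before data collection, since an unrecorded early response cannot be recovered later.

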With coughing incidence at baseline expected to be approximately 70% and a target incidence of 30%, we would need to recruit 50 patients in order to achieve an alpha or 0.05 and power of 0.9. Accounting for an exclusion of 20% (deep extubation, improper notice, failure to properly connect the system prior to the start of the case, decision by anesthesiologist to exclude patient, etc.), 60 patients would need to be recruited for this study. We will recruit 60 patients for this study.

Risks/Benefits: Describe any potential or known risks. This includes physical, psychological, social, legal or other risks. Estimate the probability that given risk may occur, its severity and potential reversibility. If the study involves a placebo or washout period, the risks related to these must be addressed in both the protocol and consent. Describe the planned procedures for protecting against or minimizing potential risks and assess their likely effectiveness. Where appropriate, discuss plans for ensuring necessary medical or professional intervention in the event of adverse effects to the subjects. Discuss the potential benefits of the research to the subjects and others. Discuss why the risks to the subjects are reasonable in relation to the anticipated benefits to subjects and others. Discuss the importance of the knowledge gained or to be gained as a result of the proposed research and why the risks are reasonable in relation to the knowledge that reasonably may result. If there are no benefits state so.

The only major risk to the patient is transient respiratory depression which may occur in 5-10% of the population. This is expected to cease promptly (within 5 minutes) after cessation of the infusion. As the patient will be monitored at all times by an anesthesia provider, the actual risk to the patient is minimal as either the patient will be assisted by a ventilator, or the patient's ventilation will be assisted by the provider. It must be stressed that assisting respiration and ventilation is one of the principal tasks of an anesthesia provider and the provider is expected to continue to manage the patient's respiration until the patient is adequate for discharge to the post-anesthesia care unit.

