Device name and indications (attach investigational device brochure)

BBraun Perfusor Space syringe pump

Is it FDA approved: (include FDA IDE Number)

1. for indication specified? If no, provide justification for proposed use and source of the device.

Yes

Risk assessment (non-significant/significant risk) - PI or sponsor needs to assess risk of a device based upon the use of the device with human subjects in a research environment.

No additional risk of use from the device.

SUBJECT CHARACTERISTICS, IDENTIFICATION AND RECRUITMENT

Subject Selection: Provide rationale for subject selection in terms of the scientific objectives and proposed study design.

The purpose of the study is to evaluate the ability of algorithm-driven administration of remifentanil to reduce coughing at emergence in patients where coughing is clinically relevant: eye surgery and head and neck procedures. Should the study be successful, this patient population will be directly impacted.

Vulnerable Populations: Explain the rationale for involvement of special classes of subjects, if any. Discuss what procedures or practices will be used in the protocol to minimize their susceptibility to undue influences and unnecessary risk (physical, psychological, etc.).

Not applicable

Number of Subjects: What is the anticipated number of subjects to be enrolled at UVM/UVM Medical Center and in the case of a multi-center study, with UVM/UVM Medical Center as the lead, the total number of subjects for the entire study.

60 patients will be recruited for the study.

Inclusion/Exclusion Criteria: Eligibility and ineligibility criteria should be specific. Describe how eligibility will be determined and by whom. Changes to the eligibility criteria at a later phase of the research have the potential to invalidate the research.

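### The 20% exclusion allowance was added to 50 rather than divided out, so 60 recruits leave 48 evaluable patients, not 50

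*Protocol*

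**What the plan says.** The sample-size paragraph under Statistical Considerations starts from the expected cough incidences: "With coughing incidence at baseline expected to be approximately 70% and a target incidence of 30" per cent. From these it concludes that "we would need to recruit 50 patients in order to achieve an alpha or 0.05 and power of 0.9".

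It then applies an allowance, "Accounting for an exclusion of 20" per cent, and gives as reasons "deep extubation, improper notice, failure to properly connect the system prior to the start of the case, decision by anesthesiologist to exclude patient", among others. The result is that "60 patients would need to be recruited for this study". The Number of Subjects section repeats the total: "60 patients will be recruited for the study".

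On timing, the Procedures section says "Patient who agree to participate in the study will be randomized to receiving either a placebo or remifentanyl", and only afterwards describes connecting the pump in the operating room. Procedures and Withdrawal Procedures both remove patients who are extubated deep or whose surgery ends too soon, and these patients receive neither drug nor placebo. Neither section mentions replacing them.

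**The concern.** An exclusion rate is a share of the patients recruited. To end with a required number after losing a fraction d, that number is divided by (1 − d). Multiplying by (1 + d) always falls short, because the loss then acts on the larger total.

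The figure of 60 looks like the multiplied form. If so, the trial misses its own evaluable target under its own assumption. In a trial of about 25 patients per arm there is little reserve, and the error pushes power down. The figure also fixes the recruitment total in two sections.

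**Working it through.** **Inputs from the protocol.** Cough incidence 70% on placebo and 30% as the target; alpha 0.05; power 0.9; 50 patients needed; 20% exclusion; 60 to recruit; Fisher exact test for the incidence of cough. The protocol states neither the sidedness of the test nor the allocation ratio. I assume 1:1 and show both one- and two-sided results.

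**Reproducing the 50.** The usual normal-approximation formula with pooled variance under the null is

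n per arm = [z(α)·√(2·p̄·(1 − p̄)) + z(β)·√(p1(1 − p1) + p2(1 − p2))]² / (p1 − p2)²

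with p̄ = 0.5, p1 = 0.7 and p2 = 0.3.

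- One-sided: [1.645·√0.50 + 1.282·√0.42]² / 0.16 = 24.8, so 25 per arm and 50 in total. This matches the protocol.
- Two-sided: the same formula with 1.960 gives 30.7, so 31 per arm and 62 in total. This does not match.

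**Reproducing the 60.** 50 × (1 + 0.20) = 60, exactly the protocol's figure.

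**Applying the stated exclusion to 60.**

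- Evaluable: 60 × (1 − 0.20) = 48, or 24 per arm.
- Recruitment that keeps 50: 50 / (1 − 0.20) = 62.5, so 63, or 64 for equal arms.
- Exclusion that 60 can absorb: (60 − 50) / 60 = 16.7%.

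**Power at 70% against 30%.**

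| Basis | 25 per arm (50) | 24 per arm (48) | Loss, points |
|---|---|---|---|
| Fisher exact, two-sided | 78.2% | 75.0% | 3.3 |
| Fisher exact, one-sided | 85.9% | 83.6% | 2.3 |
| Normal approximation, two-sided | 82.8% | 81.2% | 1.6 |
| Normal approximation, one-sided (the basis that gives 50) | 90.2% | 89.0% | 1.1 |

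The Fisher figures come from exact enumeration over all outcomes, rejecting when p ≤ 0.05. Losses are taken from unrounded values.

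**Chance of reaching 50 evaluable.** If each recruit is excluded independently with probability 0.20, the evaluable number is binomial with success probability 0.80. The probability of at least 50 evaluable is 32% with 60 recruits, 62% with 63 and 71% with 64. Even the consistent figure does not guarantee 50. With 60, however, the target is missed about two times in three.

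**The case against.** The strongest objection is that the effect is minor. Two evaluable patients are at stake. On the one-sided normal basis that reproduces 50, power drops by about one point and the stated 90% is nearly met. The 20% is a rough planning figure with no supporting data, and 16.7% lies within any reasonable uncertainty about it. This stands as a statement of size, but it does not make the figures agree with each other.

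A second objection is that setting 75% against the stated 90% overstates the slip. That is correct if the whole gap is attributed to it. On the two-sided Fisher test about 12 of the 15 points (90% to 78.2%) come from the base figure of 50, and only about 3 come from the allowance.

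A third is that the 20% could mean 10 extra patients relative to the 50 needed, which makes 60 exact. The paragraph uses the same verb for recruiting the 50 and the 60, so the denominator is not explicit. This reading is weak: the sentence presents an exclusion rate, and the listed reasons arise in patients already randomized. Even if it was intended, 10 out of 60 is 16.7%, and the sentence would still need rewording.

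Finally, writing 75% beside an unchanged 90% would leave the paragraph contradicting itself. That is a fair point about the remedy and is taken up there.

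**Conclusion.** The concern holds. At the protocol's own 20% exclusion, 60 recruits yield 48 evaluable patients rather than the 50 it says it needs. The consistent recruitment figure is 63 (64 for equal arms), and 60 covers only 16.7% exclusion.

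The cost is two evaluable patients and about 1 to 3 points of power, depending on the test. The 48, the 63 and the 16.7% need only the protocol's numbers and the reading that excluded patients come out of the 60 and are not replaced. The power figures also assume 1:1 allocation and the sidedness shown. The correction should be made, but the slip alone does not undermine the trial.

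**What to change.** Keep 60 and replace the allowance sentence under Statistical Considerations with wording such as: *Recruiting 60 patients allows for 16.7% exclusion. At 20% exclusion 48 patients are evaluable, and power for 70% against 30% is about 75% (two-sided Fisher exact test, alpha 0.05, 1:1 allocation).* State the sidedness and the allocation ratio in the same edit, and revisit the 90% claim for 50 patients so that the two power figures do not stand side by side unexplained. This takes a short change of wording and no extra patients.

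If the sponsor prefers to keep both 50 evaluable and a 20% allowance, change the recruitment total to 63, or 64 for equal arms, under both Statistical Considerations and Number of Subjects. That costs three or four more recruits. It restores the 50 but does not by itself give 90% power on a two-sided Fisher test.
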